
Inclusion Criteria
 
 
Diagnosis of cancer
 
Dyspnea with an average intensity level >3/10 on the numeric rating scale over the past week
 
Clinical or radiologic history of lung/pleural involvement (primary or metastatic), lymphangitic carcinomatosis or airway involvement secondary to tumor infiltration
 
Outpatients at MD Anderson Cancer Center seen by the Supportive Care, Rehabilitation Service, Thoracic Oncology or Pulmonary Medicine
 
Able to communicate in English
 
Karnofsky performance status <math>\geq 40\%</math>
 
Age 18 or older
 
Permission from the attending medical oncologist if the patient is currently on an interventional cancer therapy trial.
 
 
Exclusion Criteria
 
 
Delirium (i.e. Memorial delirium rating scale >13)
 
Oxygen saturation <90% despite supplemental oxygen >6L/min
 
Previous allergic reactions to dexamethasone
 
Uncontrolled hyperglycemia as defined by any blood glucose of >300 mg/dl in the past two weeks
 
Severe anemia (Hb <7g/L) not corrected prior to study enrollment (bloodwork is not required if patient did not have recent chemotherapy within last 2 weeks)
 
Post-surgical open wound that has not been healed at the time of enrollment
 
Any infection requiring antibiotics within the past 2 weeks
 
Major surgery within the past 2 weeks
 
Megestrol use at the time of study enrollment
 
Neutropenia (absolute neutrophil count < 1.0) (bloodwork is not required if patient did not have recent chemotherapy within last 2 weeks)
 
Currently on or expected to start cytotoxic chemotherapy within 1 week of study enrollment
 
Chronic obstructive pulmonary disease (COPD) exacerbation at the time of study enrollment
 
Heart failure exacerbation at the time of study enrollment
 
Chronic systemic corticosteroid use (>14 days) at the time of study enrollment
 
Unwilling to provide informed consent
 

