**Table 4. Summary of Study Assessments**

Assessments	Baseline (In person)	Day 4+/-2 (by phone)	Day 7+/-2 (In person/by phone)	Day 14+/-2 (In person/by phone)
Demographics and Cancer Diagnosis 	X			
Medication History 	X			
Karnofsky Performance Status 	X			
Dyspnea Survey 	X			
O2 saturation and Respiratory Rate	X			
Cancer Dyspnea Scale 	X	X	X	X
Edmonton Symptom Assessment Scale 	X	X	X	X
Dyspnea Numeric Rating Scale 		Daily	Assessment	
Dyspnea Borg scale 	X	X	X	X
Spirometry Measures 	X	X	X	X
EORTC QLQ-C30 	X	X	X	X
Adverse effects 		X	X	X
Global assessment 		X	X	X
Pill count			X	X
Check of blinding			X	

 patient initials, medical record number, date of birth, sex, race, education, marital status, cancer diagnosis, co-morbidities, cause(s) of dyspnea.

 medications that could be used to treat dyspnea, including scheduled and as needed opioids, bronchodilators, and steroids will be documented.

 an 11-point assessment scale that rates patients' functional status between 0% (death) and 100% (completely asymptomatic) based on their ambulation, activity level, and disease severity (Schag et al. 1984).

 characterization of patients dyspnea including the following: presence of dyspnea at rest, average dyspnea in last 24 hours, worse dyspnea in last 24 hours, best dyspnea in last 24 hours, number of episodes of exacerbation per day, triggers of breakthrough dyspnea, average duration of each episode, current treatment for breakthrough dyspnea. It also adopted 3 questions from EORTC Lung module about dyspnea.

 validated 12-item questionnaire specifically designed to assess the quality of dyspnea in cancer patients during the past few days (Tanaka et al. 2000). Each item has a score between 1 and 5, for a maximum of 60. There are sub-scores for sense of effort, anxiety, and discomfort.

 validated questionnaire that measures 10 common symptoms in the past 4 hours (pain, fatigue, nausea, depression, anxiety, drowsiness, shortness of breath, appetite, sleep, and feeling of well being) using numeric rating scales (Bruera et al. 1991).

 a 0 (no dyspnea) to 10 (worst dyspnea) categorical scale validated for rating the severity of dyspnea (Dorman et al. 2007, Gift and Narsavage 1998, Powers and Bennett 1999).

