 a 0 to 10 categorical scale for rating the severity of dyspnea. It is a ratio scale with descriptive anchors throughout the range in which a rating of 8 signifies breathlessness twice as severe as 4, which in turn is twice as severe as 2 (Dorman et al. 2007, Gift and Narsavage 1998, Kendrick et al. 2000, Powers and Bennett 1999).

 the MicroLoop Spirometer (Micro Direct Inc, Lewiston, ME) will be used at baseline, day 7 and day 14. It is approved by the American Thoracic Society and US Food and Drug Administration. Various spirometry parameters will be obtained, such as vital capacity (VC), forced expiratory volume in 1 second (FEV1), forced vital capacity

(FVC), FEV1/FVC, peak inspiratory flow, and peak expiratory flow. As an exploratory measure, patients will also be asked to use the portable Microlife PF 100 Peak Flow Meter (Microlife, Clearwater, FL) to measure peak flow and FEV1 on a daily basis.

10 a well-validated quality of life instrument for cancer patients, consisting of 30 items that encompasses 3 symptom scales (pain, fatigue, nausea/vomiting), 6 single-item symptom items, 5 functional scales (physical, cognitive, role, emotional, and social), and one scale assessing global health status/quality of life. Each scale consists of 2-5 items. All items have four response categories (not at all, a little, quite a bit, very much), except for 2 items assessing overall health status/quality of life, which use a seven-point scale.

11 adverse effects related to the use of dexamethasone, such as edema, fever, infections, insomnia, anxiety, personality change, dyspepsia will be rated using the National Cancer Institute Common Terminology Criteria for Adverse Events version 4.03.

12 patients will be asked about their dyspnea (worse, about the same, or better) comparing the level of dyspnea before and after the study (Guyatt *et al.* 1993, Redelmeier *et al.* 1996).

13 patients will be asked to record their study medication use, as well as any use of opioids and bronchodilators for relief of dyspnea.

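### Adverse effects are graded at Days 4, 7 and 14 but not at baseline, so symptoms present at entry cannot reliably be separated from those that arise on treatment

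*Combined protocol and SAP*

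**What the plan says.** In Table 4 the row "Adverse effects" is marked at Day 4, Day 7 and Day 14. Its Baseline cell is empty.

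Footnote 11 gives the content: "adverse effects related to the use of dexamethasone, such as edema, fever, infections, insomnia, anxiety, personality change, dyspepsia will be rated", using CTCAE version 4.03. It gives no pre-dose grade, no method of attribution and no rule for conditions present at entry. Section D.2 contains no adverse-effect analysis.

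Other entries bear on the state of the patient at entry:

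- The ESAS is taken at baseline and at all three later visits. It covers "pain, fatigue, nausea, depression, anxiety, drowsiness, shortness of breath, appetite, sleep, and feeling of well being" on numeric rating scales over the past 4 hours (footnote 6).
- The EORTC QLQ-C30 is taken at the same four visits, with "6 single-item symptom items, 5 functional scales (physical, cognitive, role, emotional, and social" among its scales (footnote 10).
- Footnote 1 records "cancer diagnosis, co-morbidities, cause(s) of dyspnea" at baseline, ungraded.
- Table 2 excludes "Any infection requiring antibiotics within the past 2 weeks".

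Sections C.1 and C.7 set 20 patients per arm, a blinded placebo-controlled week, and then a week in which both arms take dexamethasone.

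**The concern.** A grade first taken on Day 4 cannot show whether the symptom began before or after the first capsule. Some background is likely on the protocol's own account. Section B.1 links dyspnea to anxiety, which is one of the listed effects. Table 2 admits patients with a Karnofsky status as low as 40%. It excludes systemic corticosteroid use only beyond 14 days, so a patient already taking a steroid for a shorter time can enter.

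At stake is how far the adverse-effect rates can be read. Section C.1 says the pilot is meant to inform a larger confirmatory trial, and that trial will want to know how often these effects arise on dexamethasone. A missing pre-dose grade cannot be recovered once treatment has started.

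**Working it through.** **What is already measured at entry.** Footnote 11 names seven effects. Set against the rest of the schedule and the eligibility table:

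| Effect | Captured at entry? |
|---|---|
| Anxiety | ESAS score; also a Cancer Dyspnea Scale sub-score; no CTCAE grade |
| Insomnia | ESAS sleep score; no CTCAE grade |
| Infections | Limited by the two-week antibiotic exclusion |
| Fever | No named measure; the infection exclusion helps in part |
| Edema, dyspepsia, personality change | No named measure |

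The QLQ-C30 gives symptom and function scores but no CTCAE grade, and footnote 10 does not name its single items.

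**Inputs for the illustration.** The plan states no adverse-effect rate, so there is no figure of its own to reproduce. From the plan: n = 20 per arm. Assumed, because the documents give nothing: prevalence at entry b, shown from 10% to 60%; new onset among patients free of the symptom, 30% on dexamethasone and 15% on placebo. Symptoms present at entry are taken to persist, and worsening is ignored.

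**Formulas, all over the 20 patients randomised per arm.**

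- Raw rate = b + (1 − b) × i, where i is the new-onset rate.
- Rate of new events = (1 − b) × i.
- Expected arm difference, either way = (1 − b) × (0.30 − 0.15).
- SE of the difference between rates p and q = √{[p(1 − p) + q(1 − q)]/20}.

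At b = 30%:

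- Raw: 0.30 + 0.70 × 0.30 = 51.0% and 0.30 + 0.70 × 0.15 = 40.5%. Difference 10.5 points, ratio 0.510/0.405 = 1.26. SE = √[(0.2499 + 0.2410)/20] = 15.7 points.
- New events: 0.70 × 0.30 = 21.0% and 0.70 × 0.15 = 10.5%. Difference 10.5 points, ratio 2.0. SE = √[(0.1659 + 0.0940)/20] = 11.4 points.

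Across the range:

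| b | Raw rates | Raw ratio | New-event rates | Difference, both ways | SE raw | SE new |
|---|---|---|---|---|---|---|
| 10% | 37.0% v 23.5% | 1.57 | 27.0% v 13.5% | 13.5 points | 14.4 | 12.5 |
| 30% | 51.0% v 40.5% | 1.26 | 21.0% v 10.5% | 10.5 points | 15.7 | 11.4 |
| 60% | 72.0% v 66.0% | 1.09 | 12.0% v 6.0% | 6.0 points | 14.6 | 9.0 |

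The new-event ratio is 2.0 throughout. Symptoms present at entry make up 27% (0.10/0.37) to 83% (0.60/0.72) of the raw dexamethasone rate.

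**Chance imbalance at entry.** The SD of the baseline difference between arms is √[2b(1 − b)/20]: 12.6 points at b = 20%, 15.5 at 40% and 60%, and at most 15.8 at 50%. From the exact binomial distribution, an imbalance of at least 20 points (4 patients of 20) occurs in 16% of trials at b = 20% and in 26% at 40% or 60%.

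**Open-label week.** Both arms are on dexamethasone, so no concurrent placebo group exists. For the placebo arm, Day 7 is a pre-drug CTCAE grade if it is taken before the first open-label dose. For the dexamethasone arm every scheduled grade comes after the first dose.

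**The case against.** Randomisation and blinding protect the main contrast. In the first week placebo patients carry the same expected background and are rated by blinded staff, so over all patients the expected risk difference is the same with or without a baseline grade. This stands. A reader might infer that the 15-point onset difference is diluted to 13.5, 10.5 or 6.0 points by counting entry symptoms. That compares different denominators: 15 points is the difference among patients free of the symptom at entry, and the smaller figures are over everyone randomised.

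A reader might also infer that entry symptoms will be counted as dexamethasone effects. The documents do not say so. Footnote 11 limits rating to "adverse effects related to the use of dexamethasone", which already asks the rater for a judgement of attribution; section C.11 speaks of effects that patients develop; and D.2 has no counting rule. Miscounting is a risk, not the plan. Still, a rater asked on Day 4 about edema or dyspepsia has no scheduled earlier grade on which to base that judgement.

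Anxiety, sleep and infection are partly covered at entry, which narrows the gap without closing it. A baseline grade would not supply a comparator for the open-label week; it would supply only a pre-drug reference.

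Finally, none of the five objectives concerns adverse effects, no test or decision rule uses these rates, and section C.7 describes the study as exploratory. This stands and limits the severity.

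**Conclusion.** The gap is real and modest. No scheduled measure gives a CTCAE grade before the first dose, and for edema, fever, dyspepsia and personality change no baseline measure is named. Entry symptoms therefore cannot reliably be told apart from treatment-emergent ones.

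The consequences are inflated per-arm rates, a relative risk pulled towards 1, and noise that cannot be adjusted away at 20 per arm. They do not include an expected bias in the blinded week's absolute risk difference. The per-arm rates are least interpretable in days 7 to 14 in the dexamethasone arm, where there is neither a placebo group nor a pre-drug grade.

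The sizes rest on assumed prevalence and onset rates and on entry symptoms persisting; they show scale and are not estimates for this population. The missing baseline cell and the missing counting rule rest on no assumption. Severity is low to moderate: the primary outcome is completion of the dyspnea NRS at Day 7, and nothing here affects it.

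**What to change.** Add an X in the Baseline column of the adverse-effects row of Table 4, and have the footnote 11 items graded by CTCAE v4.03 before the first dose. Add to section D.2 that a reported adverse effect is one that is new, or worsened in grade, relative to baseline, tabulated by arm and by phase. For the placebo arm's open-label week the reference should be the Day 7 grade, taken before the first open-label dose.

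The cost is a few minutes at a baseline visit that already takes place in person, plus this definition in the analysis section. No sample size, objective or other assessment changes.

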### 3.0 Experimental Approach

**C.1. Overall Study design.** This is a 2-arm, double blind, parallel randomized controlled trial of dexamethasone and placebo for cancer patients with dyspnea (Figure 1). The main goal of this study is to determine the effect size for both dexamethasone and placebo arm to inform a larger, adequately powered confirmatory randomized controlled trial. For this preliminary study, we plan to enroll 20 patients per arm, with a total of 40 patients for the entire study (see statistical considerations for more details). Patients will be randomized to either dexamethasone or placebo for 7 days in a blinded fashion; this will be followed by an open label phase in which patients in both arms would take dexamethasone for 7 days. The rationale for the open label phase is to give all patients an opportunity to try the study medication, and to examine the use of dexamethasone at a different dose as an exploratory endpoint (objective #5). Based on our experience conducting symptom control trials, we believe this study design is feasible and would not add undue burden for patients. To reimburse patients for their time and effort, we will provide a gift card for \$20 per visit (day 7+/-2 and day 14+/-2).

**C.2. Eligibility Criteria.** The eligibility criteria are shown in Table 2.

Table 2. Study Eligibility Criteria

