**C.3. Study screening.** A 2 step consent process will be used. A verbal script is provided in the Appendix P. First, a verbal consent will be obtained by the study staff to proceed with screening of potential participants for eligibility and to characterize their dyspnea using the dyspnea survey and the cancer dyspnea scale. Eligible patients will then be formally enrolled onto the study after they have signed the informed consent indicating a willingness to participate in the trial. The number of patients screened, approached, eligible and enrolled will be documented. Reasons for refusal for eligible patients will also be captured.

**C.4. Randomization.** A computer generated sequence in permuted blocks will be used to assign patients to either dexamethasone or placebo via CORE, a secured website. We will stratify by FEV1/FVC ratio (<0.8 vs.  $\geq 0.8$ ). CORE will set up a Randomization website and Investigational Pharmacy personnel will perform the randomization assignment. [name], our research manager, will provide the necessary CORE training for the research team.

**C.5. Blinding.** Both patients and the research staff conducting the assessment will be blinded to the treatment assignment. Placebo capsules identical to dexamethasone 4mg capsules in appearance and taste will be compounded by Green Park Compounding Pharmacy, and both will be dispensed by Investigational Pharmacy at MD Anderson. At the end of the blinded phase, we will assess blinding by asking patients which study arm they believe they have been randomized to.

**C.6. Research staff.** An orientation will be held with research staff involved in this study to introduce them with the study design, and standardize the provision of each intervention.

**C.7. Study Interventions.** The intervention arm will receive dexamethasone 8 mg (2 capsules of 4 mg) given orally twice a day for 4 days, then 4 mg given orally twice a day for 3 days. This dose was chosen partly based on our feasibility data demonstrating that dexamethasone improved dyspnea.

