**C.8. Medication use during study.** We will ask patients to record the use of study medications using a medication diary. We will also keep track of their adherence by asking them to bring their medication boxes for a pill count. Phone call reminders will be provided daily. To document the co-intervention effect on dyspnea, patient use of regular and breakthrough opioids (for any reason) and bronchodilators at enrollment and during the study. Patients will receive daily phone calls for reminders and assessments. They can take it as soon as possible if they forget a dose.

**C.9. Feasibility endpoints.** Our primary objective is to test the feasibility of a protocol that uses dexamethasone and placebo for dyspnea, and to determine the feasibility of these two interventions for advanced cancer patients with persistent dyspnea. We will document the following:

- Rates of recruitment and retention (see section D1).
- Reasons for refusal and dropout
- Outcome measure—we will compare the sensitivity of Numeric rating scale and Borg scale to change, and identify key measure for future study
- Participant satisfaction—participants will provide an opinion regarding their satisfaction with study overall

**C.10. Study assessments.** See Table 4 for a detailed description of all study assessments.

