**C.11. Patient Safety, Monitoring, and Confidentiality.** Prior to study initiation, all research staff participating in this study will receive an orientation to the devices and forms in this study to ensure consistent assessments. During the study, trained research staff will be performing study assessments and monitoring the patient carefully throughout the study period. In addition to daily phone calls, patients will be given the contact information of the research nurse in case they develop any significant adverse effects, and will be treated as they arise as per clinical practice. The study may be discontinued at the discretion of the treating physician or study principal investigator. Regulatory monitoring will be provided by the principal investigator, the Institutional Review Board, and the Data Safety and Monitoring Board. Patient confidentiality will be ensured by use of patient initials, secure storage of clinical data, and anonymous reporting.

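### Harms are graded only if related to dexamethasone, and the supplied plan has no all-cause or serious-event recording and no safety table by arm

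*Combined protocol and SAP*

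**What the plan says.** Table 4 (section C.10) schedules adverse effects at days 4, 7 and 14, each with a two-day window, and has no baseline entry in that row. Footnote 11 defines the content: "adverse effects related to the use of dexamethasone, such as edema, fever, infections, insomnia, anxiety, personality change, dyspepsia will be rated". Grading follows CTCAE 4.03. The list of examples is open. The footnote does not say who decides that an effect is related, or when.

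On blinding, C.5 states: "Both patients and the research staff conducting the assessment will be blinded to the treatment assignment". Under C.1 the blinded week ends on day 7, and "this will be followed by an open label phase in which patients in both arms would take dexamethasone for 7 days".

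C.11 adds daily calls and a research-nurse contact for patients "in case they develop any significant adverse effects, and will be treated as they arise as per clinical practice". On oversight it says: "Regulatory monitoring will be provided by the principal investigator, the Institutional Review Board, and the Data Safety and Monitoring Board". It does not say what is to be recorded or reported.

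C.9 lists "Reasons for refusal and dropout" among the items to document. D.2 defines a dropout as a patient without the dyspnea numeric rating (NRS) at day 7 ± 2, whatever the cause, and counts that patient as a failure. The rest of D.2 covers dyspnea, respiratory function and quality of life. It contains no analysis or table of adverse events.

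**The concern.** In a placebo-controlled phase, the sound evidence on what a drug causes is the difference between arms in all events. A collection rule that depends on relation to the drug puts a judgment, or a preset list, ahead of that comparison. Many steroid effects resemble the course of advanced cancer: fever, infection, anxiety and insomnia can come from either. Events that nobody expects of a steroid are the ones most easily left out.

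C.1 says the main goal is to inform a larger confirmatory trial. That trial will need usable harm rates for both arms as well as effect sizes. The supplied plan would yield rates for a subset of events whose boundary is not defined. The boundary could also shift at day 7, when staff and patients learn that everyone is taking dexamethasone.

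**Working it through.** The plan states no event rate or attribution share, so there is no figure of its own to reproduce. The check is a reading of the sections together, followed by an illustration on assumed rates.

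**Does each kind of event have a route into the data?**

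- *Recognised steroid effect, days 4 to 14:* graded under footnote 11.
- *Event not linked to steroids, day 7 NRS completed:* not within footnote 11, not a dropout under D.2, and no recording rule in C.11. No stated safety record.
- *Event not linked to steroids, after the day 7 window (after day 9):* the D.2 dropout definition no longer applies, and the day 14 assessment uses the same footnote. No stated safety record.
- *Death or admission that prevents the day 7 NRS:* a feasibility failure under D.2, with its reason documented under C.9, but not graded or tabulated as harm.

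**Do the two readings of footnote 11 differ?** If relatedness is judged event by event, blinded staff decide cause before recording. If the footnote means known steroid effects asked about alike in both arms, the listed effects are graded without attribution, but someone must still decide whether an unlisted event belongs. Section B.4 reports hyperglycemia, delirium and oral candidiasis among the main side effects after one week of steroids, and the footnote names none of them. A longer list would still leave out unexpected events.

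**How many events might go unrecorded?** Expected events graded = 40 × all-cause rate × share attributed. Both factors are assumptions.

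- Serious event, admission or death rate of 10%, 20% or 30%: 40 × rate = 4, 8 or 12 events.
- Half attributed to dexamethasone: 2, 4 or 6 graded.
- A quarter attributed: 1, 2 or 3 graded.

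**Effect on the difference between arms, if relatedness is judged first.** Let b be the rate of disease events in both arms, x the added rate of drug-caused events on dexamethasone, f the share of disease events labelled related (equal in both arms because staff are blinded), and s the share of drug-caused events labelled related.

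- Recorded on placebo: b·f. Recorded on dexamethasone: b·f + x·s. Recorded excess: x·s, against a true excess of x. The fraction lost is 1 − s.
- With assumed b = 30%, x = 20%, f = 20%, s = 60%: placebo 0.30 × 0.20 = 6%; dexamethasone 0.06 + 0.20 × 0.60 = 18%. The recorded excess is 12 points, against a true 20 (50% vs 30%).
- With s = 80%, the excess is 16 points (20% lost). With s = 40%, it is 8 points (60% lost).

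**Could 20 per arm show the difference?**

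- True rates: standard error = √(0.50 × 0.50/20 + 0.30 × 0.70/20) = √0.0230 = 15.2 points; 20/15.2 = 1.3.
- Recorded rates: √(0.18 × 0.82/20 + 0.06 × 0.94/20) = √0.0102 = 10.1 points; 12/10.1 = 1.2.

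Neither contrast is resolved. The 8-point loss is about half of one standard error of the true contrast (8/15.2 = 0.53).

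**The case against.** The strongest reply is that footnote 11 describes no attribution step. Its examples are non-specific events that can be graded in either arm without any view on cause, and the natural reading is a checklist of known steroid effects. For listed effects the dilution shown above would then not arise. This stands: the text does not settle the reading, so the attenuation formula is conditional.

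Second, several steroid effects that resemble disease are measured without attribution in both arms. The Edmonton scale covers sleep, anxiety, drowsiness, nausea and appetite, and the EORTC QLQ-C30 is collected on the same days. This also stands, but these are symptom scores. They do not capture infections, admissions or deaths, and they are not graded events.

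Third, a reader might infer that the arms will be compared on events filtered by presumed cause. The documents do not support that, because D.2 plans no adverse-event comparison at all. A reader might also infer that unattributed admissions and deaths are simply not counted. That is too strong: those that prevent the day 7 NRS are counted as failures with a reason, and the named oversight bodies may receive reports under rules not shown here.

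Finally, some pages were removed from the text supplied for review, and the appendices were not supplied (C.3 cites Appendix P). A serious-event procedure may exist there. Absence can be stated only for the supplied text.

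**Conclusion.** The narrow point holds on either reading. Footnote 11 defines what is graded by its relation to dexamethasone, and the supplied text provides no all-cause or serious-event recording and no safety tabulation by arm. An event that nobody links to steroids has no stated safety record if the day 7 NRS is completed or the event comes after that window.

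The size cannot be fixed from the documents. The 20% to 60% loss only restates assumed sensitivities of 80% to 40%. It applies only if relatedness is judged before recording, and it describes expectation rather than what 40 patients would reveal. The primary feasibility endpoint, completion of the day 7 NRS, is unaffected. This is a cheap improvement to the usefulness of the pilot's harm data, and it does not threaten the pilot's main conclusion.

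**What to change.** - **Footnote 11:** at the existing contacts, record every new or worsened event whatever its presumed cause and grade it by CTCAE 4.03. Add a seriousness flag that includes admissions and deaths, and keep relatedness as a separate field that does not decide whether an event is recorded.
- **Table 4:** add a baseline entry to the adverse-effects row, so that new or worsened can be judged.
- **D.2:** add a descriptive table of all-cause events by arm for the blinded phase, and a separate one for the open-label phase. No hypothesis test is needed.
- **If a serious-event procedure exists in material not supplied here:** refer to it from C.11.

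The cost is a change of wording in the footnote, the case-report form and D.2, plus the baseline entry. The scheduled assessments and daily calls are already planned. The downside is more disease-related events to log in about 40 patients.
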